#### 1 SYNOPSIS

**Title of Study:** A Multicenter, Double-blind, Randomized, Controlled, Roll-over Study of the Safety and Pain Associated with Injections of PN40082, RV001 with Topical Anesthetic or RV001 for Lip Augmentation

Name of Sponsor: Prollenium Medical Technologies Inc.

Name of Finished Product: PN40082®

**Device Composition:** PN40082 - Hyaluronic acid gel with lidocaine (0.3% w/w) RV001- Hyaluronic acid gel without lidocaine

**Objectives:** To evaluate the safety of repeat injections and pain associated with injection of PN40082 and comparative pain associated with RV001 with a topical anesthetic and RV001 for lip augmentation.

**Study Design:** This is a multicenter, double-blind, randomized, controlled, roll-over clinical study of treatment of subjects seeking lip augmentation who received treatment with either PN40082 or Restylane Silk in prior Protocol PRO 2018-02, and PN40082 in prior Protocol PRO 2018-03. Subjects meeting the inclusion/exclusion criteria will receive a single additional treatment with either RV001, RV001 with a topical anesthetic, or PN40082. The Evaluating Investigator will be blinded to the treatment. Injections of the study device will be performed by an unblinded Treating Investigator.

At each visit the blinded Evaluating Investigator evaluations and subject evaluations of the treated areas will be performed and recorded. Visits and telephone contacts will occur at:

Visit 1 / Day 1 — baseline and treatment

- Day 3 (±2 days) Safety follow-up telephone call
- Day 14 (±2 days) Safety follow-up telephone call

Visit 2 / Day 28 ( $\pm 2$  days) / Month 1 – End of Study Visit

- Day 56 (±4 days) / Month 2 Safety follow-up telephone call
- Day 168 (±7 days) / Month 6 End of Study telephone call

Efficacy evaluations are:

Subject pain score (VAS) at time of injection

Subject pain score (VAS) at 15 minutes after injection

Lip Fullness Grading Scale (LFGS) - overall lip fullness considering both lips together, fullness of the upper lip, and fullness of the lower lip

Perioral lines at rest severity scale (POL) - overall perioral lines at rest severity considering both lips together, perioral lines at rest severity of the upper lip, and perioral lines at rest severity of the lower lip

Patient Global Aesthetic Improvement (pGAI)

Investigator Global Aesthetic Improvement (iGAI)

Safety of repeat injections, comparing incidence of reported AEs from all three studies will be analyzed. Safety will be assessed by monitoring adverse events (AEs) at all study visits. Other safety evaluations are lip function, lip sensation, lip texture, lip firmness, lip symmetry, and lip movement/function.

Other evaluations are Investigator Ease of Use Assessment, Swelling Assessment, and Subject Satisfaction with Lips Assessment.

**Number of Study Centers:** Five (5) sites in the United States

**Duration of Participation:** Subjects will participate in the study for approximately six (6) months from the time they sign the informed consent form (ICF) through the final contact

**Duration of Study:** The study will require approximately 20 months from the beginning to the end of the study (first subject signing the ICF to last contact with last subject)

**Number of Subjects:** Eligible subjects from the PRO 2018-03 study will be encouraged to be retreated during their Day 168/Month 6 telephone call. It is anticipated that the number of subjects will be less than the 158 subjects enrolled in the PRO 2018-02 study.

## **Inclusion Criteria:**

1. Completed Protocol PRO 2018-03

OR

Protocol PRO 2018-02 and did not enroll in Protocol PRO 2018-03.

- 2. Men or non-pregnant or non-breastfeeding women over 21 years of age
- At PRO 2018-02 baseline visit had an overall score of very thin, or thin on the LFGS, as agreed upon by the Treating and Evaluating Investigators, and desires at least a 1point improvement in overall LFGS score; OR

Had a Fitzpatrick skin phototype IV, V or VI and has an LFGS score of thick or full, as agreed upon by the Treating and Evaluating Investigators, and desires treatment to the vermilion body of 1 or both lips

- 4. If female and of childbearing potential, a negative urine pregnancy test at Visit 1/Day 1 and the subject agrees to use adequate contraception during the study period.
- 5. Willing to give written informed consent and read and sign the Adverse Event of Special Interest (AESI) letter dated 04JUN19.

### **Exclusion Criteria:**

- 1. Women who are pregnant, lactating, or planning a pregnancy.
- 2. Subjects with a known history of allergy, anaphylaxis or hypersensitivity to injectable hyaluronic acid products, local anesthetics of the amide type such as lidocaine, or to latex.
- 3. Subjects with a significant ongoing adverse event from PRO 2018-02 or PRO 2018-03 that in the opinion of the investigator could be worsened by participation in this study.
- 4. Subjects that experienced an SAE, AESI, visual changes or other serious medical conditions during PRO 2018-02 or PRO 2018-03.
- 5. Subjects with abnormal vision evaluations (Confrontational Visual Fields, Ocular Motility) or abnormal Snellen Visual Acuity at Visit 1 pre-treatment as defined in section 7.6.5 and Appendix 5.
- 6. Subjects who are unable to withhold thrombolytics, or inhibitors of platelet aggregation or nonsteroidal anti-inflammatory drugs (NSAIDs, e.g., aspirin, ibuprofen) or other substances known to increase coagulation time (e.g., herbal supplements with garlic or gingko) within 10 days before AND after any injection session.
- 7. Subjects with clinically significant organic disease including clinically significant cardiovascular, hepatic, pulmonary, neurologic, or renal disease or other medical condition, serious intercurrent illness, or extenuating circumstance that, in the opinion of the investigator, preclude participation in the trial.
- 8. Subjects with lip tattoos, piercings, facial hair, or scars that would interfere with visualization of the lips and perioral area for the effectiveness assessments.
- 9. Subjects with abnormal lip function, with inability to effectively sip water through a straw.
- 10. Subjects with abnormal lip sensation with inability to feel a 0.4G monofilament or a cotton wisp at any site on the lip.
- 11. Subjects with moderate or severe abnormal lip asymmetry.
- 12. Subjects with any mass formation on the lip.
- 13. Subjects with dentures or any device covering all or part of the upper palate, and/or severe malocclusion or dentofacial or maxillofacial deformities as judged by the Treating Investigator. Subjects planning to undergo extensive dental procedures such as dental implants, multiple tooth extractions, or oral surgery should not participate. Minor dental procedures such as teeth cleaning and repair of caries are not exclusionary.
- 14. Subjects that have undergone facial plastic surgery or received permanent facial implants (e.g., polymethylmethacrylate, silicone, polytetrafluoroethylene, polyacrylamide, lifting threads) anywhere in the face or neck, or are planning to be implanted with any of these products during the study.

- 15. Subjects that have undergone semi-permanent dermal filler treatment (e.g., calcium hydroxylapatite, poly-L-lactic acid) in the lower face (below the orbital rim) within 12 months before enrollment or are planning to undergo such treatment during the study.
- 16. Subjects that have undergone facial tissue augmentation with fat injections, botulinum toxin injections in the lower face (below the orbital rim), mesotherapy, or cosmetic procedures in the face or neck (e.g., face-lift, laser, photo-modulation, intense pulsed light, radio frequency, dermabrasion, moderate or greater depth chemical peel, microneedling, or other ablative procedures) within 9 months before enrollment or are planning to undergo any of these procedures during the study.
- 17. that have used ANY lip filling agents within 12 months of study enrollment (hyaluronic acid products, collagen-based products, etc.) other than Investigational Device administered in PRO 2018-02 and PRO-2018-03.
- 18. Subjects that have used any lip plumping products or devices within 10 days before enrollment or are planning to use such products during the study.
- 19. Subjects that have begun using any over-the-counter (OTC) or prescription oral or topical anti-wrinkle products for the lips or around the mouth within 90 days before enrollment or are planning to begin using such products during the study (Subjects who have been on a stable regimen of such products for at least 90 days are eligible for the study and must continue their regimen throughout the study).
- 20. Subjects that have a history or presence of bleeding disorders.
- 21. Subjects that have used systemic corticosteroids or immunosuppressive medications within 30 days prior to treatment.
- 22. Subjects that are on a concurrent regimen of lidocaine or structurally related local anesthetics (e.g., bupivacaine)
- 23. Subjects that have an active inflammation (skin eruptions such as cysts, pimples, rashes, or hives), infection cancerous or precancerous lesion, or unhealed wound on the face.
- 24. Subjects that have a history of known susceptibility to keloid formation or hypertrophic scars.
- 25. Subjects that have porphyria.
- 26. Subjects that have active herpes labialias lesions at the time of injections. Subjects with a history of herpes labialis who have had four (4) or more outbreaks in the 12 months prior to enrollment are also excluded even in the absence of lesions at the baseline visit.
- 27. Subjects that have impaired cardiac conduction, severely impaired hepatic function, or severe renal dysfunction that, in the opinion of the investigator, would place them at risk of associated complications from these illnesses during the course of the study.
- 28. Subjects that have any uncontrolled disease, i.e., a condition that has not been appropriately diagnosed, evaluated, and received medically appropriate treatment or care

29. Subjects that have severe cardiovascular disease; examples include but are not limited to New York Heart Association heart failure classification III or IV, unstable angina, and internal pacemakers. Potential subjects with other significant cardiovascular diseases should be discussed with the Medical Monitor before enrolling.

## **Study Device**

PN40082: a clear, colorless gel in 1.0 mL pre-filled syringes with 25 mg/mL of stabilized hyaluronic acid and lidocaine 0.3% w/w

RV001 with a topical anesthetic: a clear, colorless gel in 1.0 mL pre-filled syringes with 25 mg/mL of stabilized hyaluronic acid to be used with LMX4 topical lidocaine

RV001: a clear, colorless gel in 1.0 mL pre-filled syringes with 25 mg/mL of stabilized hyaluronic acid to be used alone

### Statistical Methods

Safety and efficacy results will be summarized descriptively for all subjects who receive treatment in this study. Data will be summarized overall and also broken down by the treatment arm. A detailed description of statistical analysis of the data from this study will be included in a separate Statistical Analysis Plan (SAP) document.

## **Efficacy Analysis:**

Compare subject pain scores (VAS) between PN40081, RV001 with topical anesthetic, and RV001. Change from baseline will be summarized for LFGS and POL. Other efficacy variables include pGAI, iGAI, and Swelling Assessment at Visit 2/Month 1.

## **Safety Analysis:**

Safety of the treatment with PN40082 or RV001 with topical anesthetic or RV001 will be evaluated by the nature, severity, and frequency of treatment-emergent adverse events (TEAEs). All AEs that occur during the study will be recorded whether or not they are considered to be related to treatment. A description of the AE will be recorded with the date of onset, date of resolution, severity of the AE, relationship to the study device, action taken, and the outcome. The frequency and type of AEs will be evaluated for each group based on the previous treatments that they received in the PRO 2018-02 and PRO 2018-03 protocols, and the difference in AEs in this protocol (PRO 2019-02) between the subjects who received injections that contained lidocaine, and the group that was treated with topical lidocaine. Safety of repeat injections, comparing incidence of reported AEs from all three studies, PRO 2018-02, PRO 2018-03, and PRO 2019-02 will be discussed in the clinical study report. Adverse events will be coded to system organ class and preferred terms using the Medical Dictionary for Regulatory Activities (MedDRA, Version 20 or higher).

Frequency and percentage of subjects reporting treatment-emergent adverse events (TEAEs) will be tabulated overall and for each treatment in PRO 2019-02 by preferred terms and further by severity and relationship to study device. In summaries of severity and relationship, subjects reporting more than one event in a treatment arm that are mapped to the same

preferred term will be counted only once in that treatment arm under the strongest severity and relationship, respectively. In addition, visual-related TEAEs will be summarized separately by preferred term.

# 2 SCHEDULE OF ACTIVITIES

Visit Number (Month)	Visit 1	Phone Contact	Phone Contact	Visit 2 (Mo 1)	Phone Contact	Phone Contact	Unsched Visit
Scheduled Day(s)	Day 1	Day 3	Day 14	Day 28	(Mo 2) Day 56	(Mo 6)  Day 168	
Scheduling Window	± 14 days of Day 168/Month 6 telephone call for PRO 2018-03	·	± 2 days	± 2 days	± 4 days	± 7 days	
Informed consent and AESI Letter	X						
Medical history/ demographics	Xª						
Vital Signs	X						
Vision evaluations (Snellen visual acuity, confrontational visual fields, ocular motility) b	X			X			Xc
Concomitant medication/ Treatment	X	X	X	X	X	X	X
Inclusion/exclusion criteria review	X						
Urine pregnancy test d	X						
Reason for study participation question	X						
Lip Fullness Grading Scale (LFGS) (overall, upper lip, and lower lip)	X			X			X c
Perioral lines at rest severity scale (POL) (overall, upper lip, and lower lip)	X			X			Xc
Lip function	Xe			X			Xc
Lip sensation	Xe			X			Xc
Lip texture	Xe			X			Xc
Lip firmness	Xe			X			Xc
Lip symmetry	Xe			X			Xc
Lip movement/function	X e			X			X c
Patient GAI (pGAI)	Xe			X			Xc
Swelling Assessment	$X^{e}$			X			X c
Investigator GAI (iGAI)	Xe			X			Xc
Subject Satisfaction with Lips	Xe			X			X c
Randomization	X						
Application of Lidocaine cream or inert cream 15 minutes prior to treatment	X						
Treatment with study device	X						
Investigator Ease of Use Assessment	X						
Subject Pain score VAS (immediately after treatment, 15 minutes after treatment)	X						
Subject Pain score VAS				X			X
Treatment question				X			
Adverse event assessment Subject Diary	X Dispense	X	X	X Collect	X	X	X
, ,	F						

Note: The timing of each visit is relative to Day 1, which is defined as the day the subject is treated.

a. To be updated if/as needed for changes since Visit 1 of *PRO 2018-02*.

b. To be performed prior to any treatment and repeated 30 minutes following any treatment and all follow-up visits.

- c. If/as needed
- d. For women of childbearing potential, to be completed prior to enrollment.e. To be performed prior to treatment

# 4 LIST OF ABBREVIATIONS AND DEFINITIONS OF TERMS

Term	Definition
AE	adverse event
AESI	Adverse Event of Special Interest
CFR	Code of Federal Regulations
CRF	case report form, paper or electronic
DCF	data correction form
EOS	end of study
FDA	Food and Drug Administration
GCP	Good Clinical Practice
ICF	informed consent form
ICH	International Council for Harmonisation
iGAI	Investigator Global Aesthetic Improvement
IRB	Institutional Review Board
IUD	intrauterine device
LFGS	Lip Fullness Grading Scale
MedDRA	Medical Dictionary for Regulatory Activities
OTC	over-the-counter
pGAI	Patient Global Aesthetic Improvement
PI	principal investigator
POL	Perioral Lines Severity Scale
SAE	serious adverse event
SAR	suspected adverse reaction
SOP	standard operating procedure
TEAE	treatment-emergent adverse event
VAS	visual analog scale

#### 5 INTRODUCTION

PN40082 is a stabilized hyaluronic acid dermal filler with lidocaine. RV001 is a stabilized hyaluronic acid dermal filler. RV001 is highly hydrophilic and is osmolality balanced, resulting in less swelling response to injections and less pain on injection.

The purpose of this study is to evaluate the safety of repeat injections and pain associated with injection of PN40082 and comparative pain associated with RV001 with a topical anesthetic and RV001 for lip augmentation in subjects who participated in PRO 2018-02 and PRO 2018-03.

### 6 STUDY OBJECTIVES

To evaluate the safety of repeat lip augmentation treatment and pain associated with injection and safety of PN40082, RV001 with topical anesthetic, or RV001 for lip augmentation.

## 7 INVESTIGATIONAL PLAN

## 7.1 Overall Study Design

This is a multicenter, double-blind, randomized, controlled, roll-over study of the safety and pain associated with injections of PN40082, RV001 with topical anesthetic, or RV001 for lip augmentation.

Visits and telephone contacts will occur at:

Visit 1 / Day 1 - baseline and treatment.

- Day 3 (±2 days) Safety follow-up telephone call
- Day 14 (±2 days) Safety follow-up telephone call

Visit 2 / Day 28 ( $\pm 2$  days) / Month 1 – End of Study (EOS) Visit

- Day 56 (±4 days) Safety follow-up telephone call
- Day 168 (±7 days) End of Study telephone call

Efficacy evaluations are:

Subject pain score (VAS) at time of injection, 15 minutes after injection and at Visit 2.

Lip Fullness Grading Scale (LFGS) - overall lip fullness considering both lips together, fullness of the upper lip, and fullness of the lower lip

Perioral lines at rest severity scale (POL) - overall perioral lines at rest severity considering both lips together, perioral lines at rest severity of the upper lip, and perioral lines at rest severity of the lower lip

Patient Global Aesthetic Improvement (pGAI)

Investigator Global Aesthetic Improvement (iGAI)

Safety will be assessed by monitoring adverse events (AEs) at all study visits. Adverse events of special interest, including any changes in vision and any events attributable to an embolic or ischemic cause (e.g., skin infarction), will be monitored. Other safety evaluations are lip function, lip sensation, lip texture, lip firmness, lip symmetry, and lip movement/function.

Other evaluations are Investigator Ease of Use Assessment, Swelling Assessment, and Subject Satisfaction with Lips Assessment.

## 7.2 Beginning and End of Study

A subject is considered to be enrolled in the study when he/she has provided written informed consent.

A subject is considered to have completed the study after he/she has completed the Day 168 Month 6/End of study telephone call.

A subject is considered to have withdrawn after he/she has withdrawn consent or has been withdrawn under the conditions specified in Section 7.3.3.

A subject is considered to have been lost to follow-up if he/she cannot be contacted by the investigator. The investigator will document efforts to attempt to reach the subject at least twice by telephone and will send a certified letter before considering the subject lost to follow-up. The end of participation for a subject lost to follow-up is documented as the date of the certified letter.

Each subject will be monitored for the occurrence of AEs, including serious adverse events (SAEs), starting immediately after treatment initiation. Each subject will be followed for safety monitoring until he/she is discharged from the study.

Follow-up procedures related to pregnancy, AEs, or SAEs may continue beyond the end of the study.

Each subject will participate in the study for approximately 6 months from the time he/she signs the ICF through the final contact. After determination of eligibility at Visit 1/Day 1, each subject will be treated with study device.

It is anticipated that the duration of this study will be 20 months from the beginning to the end of the study (first subject signing the ICF to last contact with last subject).

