### 7.4.3 Study Device Administration

Subjects are physically masked (blindfolded) just prior to and during all injection procedures including the application of the LMX4 or inert cream to prevent observation of the syringes containing study device and the topical product. Any unblinded investigators and staff should be reminded NOT to discuss the treatment in the presence of the subject. Subjects will maintain the unique subject number previously assigned in Protocol PRO 2018-02 and PRO 2018-03.

The subject should be positioned in a seated position and may be reclined to as much as 45°.

Any makeup should be removed with a gentle cleanser or a specific makeup remover product (such as Neutrogena Cleansing Makeup Remover Facial Wipes).

The non-vermillion areas of the upper and lower lips should be prepared by gentle washing with a surgical scrub product (Chlorhexidine, Technicare, etc.).

To maintain the subject blinding, the upper and lower lip, upper and lower vermillion and any planned injection areas in or around the mouth corners should be covered with a liberal application of either the Sponsor provided inert cream or the topical anesthetic according to the randomization code. The designated cream product should be applied in a layer thick enough

that no skin or lip color is visible through the product. Investigators should use as much cream as necessary to achieve this result and not be limited to the contents of one tube of product.

Wait 15 minutes before treatment administration.

The anesthetic cream or inert cream should be removed by wiping firmly with a dry gauze before injecting. Only the area to be immediately treated should be wiped clear of cream. Areas not yet treated should remain covered with cream until moments prior to undergoing injection.

To prepare the syringes for use, the investigator should attach one of the needles included in the subject study device kit in a firm manner. The plunger should be gently depressed to express any unwanted air until a small droplet of implant material appears at the tip of the needle.

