## 7.7.1 Visit 1/Day 1: Treatment

Visit is  $\pm 14$  days of Day 168/Month 6 telephone call for PRO 2018-03 or for subjects enrolled from PRO 2018-02, Visit 1 is Day 1.

- Obtain written informed consent and read and sign the AESI letter dated 04JUN19.
- Update the medical history and demographic information as needed from entry to Protocol PRO 2018-02 and PRO 2018-03
- Perform vital signs (temperature, heart rate, blood pressure, and respiratory rate)
- Vision evaluation (Snellen visual acuity, confrontational visual fields, ocular motility)
- Obtain/record concomitant medications/treatments

- Evaluate inclusion/exclusion criteria
- Perform urine pregnancy test for all women of childbearing potential
- Reason for study participation question
- LFGS assessment
- POL assessment
- Lip function evaluation prior to treatment administration
- Lip sensation evaluation prior to treatment administration
- Lip texture evaluation prior to treatment administration
- Lip firmness evaluation prior to treatment administration
- Lip symmetry evaluation prior to treatment administration
- Lip movement/function prior to treatment administration
- pGAI assessment prior to treatment administration
- iGAI assessment prior to treatment administration
- Swelling assessment prior to treatment administration
- Subject satisfaction with lips (VAS) prior to treatment administration
- Treatment administration waiting 15 minutes after lidocaine cream or inert cream application
- Investigator Ease of Use assessment
- Subject Pain Score immediately after treatment (VAS)
- Subject Pain Score 15 minutes after treatment (VAS)
- Vision evaluation (Snellen visual acuity, confrontational visual fields, ocular motility) 30 minutes post treatment.
- Assess AEs
- Dispense subject diary card
- Schedule next visit
- Complete CRFs

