#### 7.9.5 Monitoring Adverse Events

Each subject will be monitored for the occurrence of AEs, including SAEs, immediately after treatment initiation. Each subject will be followed for safety monitoring until discharged from the study. Follow-up procedures related to pregnancy or AEs or SAEs may continue beyond the end of the study.

Subjects will be questioned and/or examined by the investigator or a qualified designee for occurrence of AEs throughout the study. The presence or absence of specific AEs should not be elicited from subjects. In addition, subjects will be instructed to record AEs on the subject diary card during the 2 weeks after treatment, and on the subject diary card dispensed at Visit 2 for the remainder of the study. Subjects having AEs will be monitored with relevant clinical assessments and laboratory tests, as determined by the investigator.

AEs, actions taken as a result of AEs, and follow-up results must be recorded on the CRF, as well as in the subject's source documentation.

For all AEs that require the subject to be withdrawn from the study and SAEs, relevant clinical assessments will be repeated as clinically appropriate until final resolution or stabilization of the event(s).

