#### 7.9.6.2 Assessment of Causality

A medically qualified investigator must assess the relationship of any AE (including SAEs) to the use of the study device as unlikely related, possibly related, or probably related based on available information, using the following guidelines:

Unlikely related: no temporal association, or the cause of the event has been identified, or the study device cannot be implicated based on available information

Possibly related: temporal association but other etiologies are likely to be the cause; however, involvement of the study device cannot be excluded based on available information

Probably related: temporal association, other etiologies are possible, but unlikely based on available information

[figure not shown]

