#### 8.1 Analysis Populations

Safety and efficacy results will be summarized descriptively for all subjects who receive treatment in this study.

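### Adverse-event start, the analysis set and causality scoring do not clearly cover the randomized cream, which is applied 15 minutes before injection

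*Combined protocol and SAP*

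**What the plan says.** Section 7.2 monitors each subject for AEs "starting immediately after treatment initiation". Section 7.9.5 repeats the anchor: "Each subject will be monitored for the occurrence of AEs, including SAEs, immediately after treatment initiation". Neither defines treatment initiation. TEAE is expanded in the abbreviation list but never given an operational definition.

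The cream is randomized: Section 7.4.3 has LMX4 or the inert cream applied according to the randomization code. The schedule gives it its own row, "Application of Lidocaine cream or inert cream 15 minutes prior to treatment", distinct from the row for the study device. Section 7.4.3 then instructs "Wait 15 minutes before treatment administration", and Section 7.7.1 lists "Treatment administration waiting 15 minutes after lidocaine cream or inert cream application".

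Section 8.1 has one analysis set: "Safety and efficacy results will be summarized descriptively for all subjects who receive treatment in this study".

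On causality, Section 7.9.6.2 requires the "relationship of any AE (including SAEs) to the use of the study device as unlikely related, possibly related, or probably related". Section 7.6.1 has the blinded Evaluating Investigator judge relationship to the device or to the injection procedure. Section 7.9.6.3 refers expectedness to Appendices 2 and 3 (the two gels) and omits Appendix 4 (the LMX4 insert). Section 8.3 tabulates TEAEs by relationship to the study device.

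The synopsis and Section 7.9.1 plan to evaluate the difference in AEs between subjects injected with lidocaine-containing product and the topical lidocaine group.

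**The concern.** The topical anesthetic is half of what distinguishes one randomized arm, and the protocol intends to compare its AEs with those of injected lidocaine. That comparison needs events after the cream to be collected, counted in a defined set, and attributable to the cream. On the schedule's usage, each of those three steps starts from the injected gel.

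Two kinds of event are at risk in collection: a reaction that appears and resolves during the 15-minute wait, and a reaction that leads to the injection not being given. A third problem, attribution, does not depend on timing. A cream reaction that is recorded and correctly recognised still has no relatedness category of its own, and under Section 7.9.6.2 the lowest grade is available once an event's cause is known. Section 7.9.7 also limits the sponsor's FDA notification of SAEs, in one sentence, to device-related ones, so the missing category reaches beyond the tables.

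**Working it through.** The protocol states no figure to reproduce on this point. The check compares definitions, followed by a calculation of scale.

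1. **Does treatment include the cream?**
   - Usage that excludes it: the schedule, Section 7.4.3 (the wait instruction) and Section 7.7.1 all place the cream 15 minutes before treatment. Section 7.6.1 also names the topical product separately from the study device.
   - Usage that includes it: Section 7.4.2 randomizes to treatments, one of which is RV001 with a topical anesthetic; Section 7.9.1 describes a group treated with topical lidocaine; the synopsis lists RV001 with topical anesthetic under the study device heading.
   - Result: the term has two senses, and Sections 7.2, 7.9.5 and 8.1 do not say which applies.

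2. **What follows on the schedule's sense?** Monitoring begins after the cream wait. A transient reaction during the wait precedes it. Even if such an event is written down, the safety tables are of treatment-emergent events, and that term inherits the same ambiguity. A subject given cream but not injected has not received treatment and falls outside the Section 8.1 set.

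3. **What follows on the wider sense?** Both gaps close. The timing and analysis-set problems are therefore conditional on the reading.

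4. **Does causality depend on the reading?** Less so. Section 7.9.6.2 names only the study device; Section 7.6.1 adds the injection procedure. The two disagree, and neither names the cream. Section 7.9.6.3 omits the LMX4 insert, although that insert lists redness, irritation, swelling and pain, which overlap with the expected injection-site events in Section 7.9.3.1. Without a separate field, the tables cannot tell these sources apart.

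5. **Scale.** Inputs: the synopsis anticipates fewer than 158 subjects, so at most 157; allocation is 1:1:1 (Section 7.4.2).
   - Per arm: 157 / 3 = 52.3, about 52.
   - Weight of one subject in an arm's incidence: 1 / 52 = 1.9 percentage points.
   - The documents give no rate of cream reactions. Assuming a rate r of any reaction within the 15 minutes, the expected number is 52r and the chance of at least one is 1 − (1 − r)^52:

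| Assumed r | Expected number | Chance of at least one |
|---|---|---|
| 1% | 0.52 | 41% |
| 2% | 1.04 | 65% |
| 5% | 2.6 | 93% |
| 10% | 5.2 | 99.6% |

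These count reactions that occur in the window, not reactions lost. A reaction still present after injection falls inside monitoring, so the number unrecorded cannot be obtained from these figures.

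**The case against.** A reader might infer that cream reactions are simply missed. The documents do not support that. The synopsis and Section 7.9.1 require every AE during the study to be recorded whatever its relation to treatment; enrolment is at consent, before any cream; the AE definition in Section 7.9.3.1 covers drug or device; Section 7.6.1 has AEs noticed by the Treating Investigator passed on for documentation; and Visit 1 includes an AE assessment that would catch a persisting reaction. This stands, and it confines the timing risk to transient reactions and to subjects not injected. It does not remove that risk, because the record-everything rule and the later start in Sections 7.2 and 7.9.5 are never reconciled and the tables are of treatment-emergent events.

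A reader might also infer that the comparison is tilted in favour of the LMX4 arm. That is not shown. Causality is judged by a blinded evaluator, every arm receives a cream so a late start applies to all three, and the planned lidocaine comparison is of AEs regardless of relationship. Relatedness enters only the further breakdown in Section 8.3.

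On causality, Section 7.4.3 counts cream application among the injection procedures when describing the blindfold. Read with Section 7.6.1, that could bring the cream within a scored category. It is a possible reading, but it comes from a blinding instruction, and Section 7.9.6.2, which defines the scale, has no such category.

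Finally, exclusion criterion 2 removes subjects with known hypersensitivity to amide anesthetics, so serious reactions may be few.

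**Conclusion.** The causality gap holds on the text: two sections disagree on what is scored, neither names the randomized topical product, expectedness omits its insert, and a recognised cream reaction can be tabulated as unlikely related. The AE-start and analysis-set gaps are real ambiguities, not settled losses; they arise if treatment carries the meaning it has in the schedule.

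The size is bounded only loosely. One subject carries 1.9 percentage points in an arm of about 52, assuming 157 subjects split equally. That is a weight, not an estimate of loss. Neither the number of events affected nor the direction of any bias can be derived from the documents. The point is still worth acting on because the protocol sets itself an injected-versus-topical lidocaine safety comparison and the remedy is small.

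**What to change.** - **Sections 7.2 and 7.9.5:** start AE collection at application of the first randomized product, cream or device, and define treatment-emergent from the same moment. This aligns them with the record-all-AEs rule in Section 7.9.1.
- **Section 8.1:** name a safety set of all subjects who receive cream or injection. The current sentence serves both safety and efficacy, so it needs splitting.
- **Section 7.9.6.2:** reconcile with Section 7.6.1 by scoring relationship separately to the device, the topical product and the injection procedure. Tabulate all three in Section 8.3. The evaluator can score the topical product without knowing whether it was LMX4 or inert, so the blind is unaffected.
- **Section 7.9.6.3:** add Appendix 4 to the reference safety information.

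The cost is wording in these sections and two extra CRF fields. No dose, procedure or visit changes.
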